#### Endpoints

**Primary:** Evaluate time to return of lower extremity motor function between mepivacaine and low-dose bupivacaine spinal anesthetic among patients undergoing primary THA and TKA. This will be assessed by measuring time from spinal anesthetic administration to postoperative achievement of Bromage 0 function (return of spontaneous ankle, knee, and hip movement) in the non-operative extremity.

**Secondary:** Evaluate postoperative outcomes potentially related to anesthetic administration including pain scores, opioid consumption, urinary retention, transient neurologic symptoms, length of PACU stay, length of hospital stay, time to participation in physical therapy and walking distance with physical therapy. This will be determined by nurse and physical therapy charting and review of the medical record.

#### Analysis

[name] will lead the data analysis effort. All pre- and post-operative data will be entered by the study coordinator into standardized Excel Spreadsheets and RedCap forms as appropriate. The data will primarily be collected by the lead Study Coordinator and checked for accuracy and completeness by [name]. All outcomes will be reported descriptively using appropriate summary statistics, including 95% confidence intervals, where appropriate. Because this is a prospective, randomized trial, no formal between-group comparisons of baseline covariates will be performed. The primary study outcome will be time to return of full lower extremity motor function. Secondly, we will assess a variety of both continuous and categorical outcomes between groups including pain scores, opioid consumption, urinary retention, transient neurologic symptoms, length of PACU stay, length of hospital stay, time to participation in physical therapy and walking distance with physical therapy. Outcomes measured on a continuous scale, including time to full lower extremity motor function, length of PACU stay and hospital stay, time to participation in physical therapy, and walking distance will be compared between the 2 study groups using two-sample t-tests if the data are sufficiently normally distributed; otherwise non-parametric Wilcoxon rank sum tests will be used. Ordinal variables such as pain scores will be analyzed using non-parametric Wilcoxon rank sum tests. Binary and nominal categorical outcomes will be compared between the study groups using chi-square tests or Fisher's exact tests, if low expected cell counts are observed. All statistical tests will be two-sided and the threshold of statistical significance will be set at  $\alpha = 0.05$ .

While it is expected that the study enrollment will be complete in approximately 4 to 6 months, one interim analysis will be performed at 2 months, or once half the subjects have been enrolled, whichever comes first. The Lan-DeMets alpha spending function with O'Brien-Fleming type boundaries will be utilized to maintain the overall type 1 error rate at  $\alpha=0.05$ , regardless of the timing of the analysis.

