**In Hospital Evaluation:** A standardized study card will be used to track patients throughout their various phases of care. At the time of discharge, the cards will be returned to the study coordinator for data entry in a secure spreadsheet available only to study staff. The study will begin with the anesthesiologist recording the time the spinal anesthetic is administered. The anesthesiologist will also record the time of incision, time of surgical closure, and time leaving the OR. The PACU nursing staff will then record the time of PACU entry and exit as well as the status of lower extremity function in the non-operative lower extremity at 15 minute intervals. The choices will be Bromage 3 (no movement), Bromage 2 (ankle movement only), Bromage 1 (ankle and knee movement), Bromage 0 (ankle, knee, and hip movement). Once the patient transitions to the general inpatient floor, the nursing staff will be responsible for recording motor function in a similar fashion at 15 minute intervals until the patient achieves Bromage 0 status. The physical therapy team will be responsible for recording the time of the first physical therapy session and the distance the patient ambulates during this session. Additional data points to be recorded by nursing staff will be total opioid consumption in the first 24 hours after surgery, pain scores, presence of nausea and/or vomiting, presence of orthostatic hypotension, and length of hospital stay. TNS will be evaluated twice, once during hospitalization by either the orthopedic or anesthesia team rounding on the patient on post-operative day one and a follow-up phone call performed on POD 6-9 by a study member not blinded to patient assignment. A standardized questionnaire will be used to determine the presence of symptoms of backache. TNS will be defined as new onset of back pain that radiates

bilaterally to buttock or distally. Back pain that does not meet these criteria will not be considered TNS. (ref. Anesth Analg 2005;101:661-5)

**Follow-up Evaluation:** Assessment will only take place during the hospitalization for the intended surgery. There will be a single phone call during post-operative day 6-9 for assessment of TNS.

**Resources:** *Describe the available resources to conduct the research (personnel, time, facilities, mentor commitment, etc.):*

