The Co-Principal Investigator orthopedic surgeons maintain high volume practices specializing in TKA and THA. This group of surgeons works exclusively with the Co-Principal Investigator anesthesiologists who specialize in the care of TKA and THA patients.

[name] is an orthopedic surgery resident who will assist with study execution and data analysis. A study coordinator in the department of orthopedic surgery will work with the residents and the midlevel providers for the orthopedic consultants to enroll patients at the preoperative visit. Standardized study cards will be created for patients enrolled in the study so that PACU and floor nursing staff as well as physical therapists can track relevant study endpoints. These cards will be returned to the study coordinator for data entry.

[name] is a master level statistician in the Division of Biomedical Statistics and Informatics with significant experience in the department of orthopedics and executing randomized clinical trials. He will serve as the lead statistician.

All funding for the study including statistical and coordinator FTE will be covered by the Department of Orthopedic Surgery and research royalty accounts of the Co-Principal Investigators.

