### Subject Information

*Target accrual is the proposed total number of subjects to be included in this study at Mayo Clinic. A "Subject" may include medical records, images, or specimens generated at Mayo Clinic and/or received from external sources.*

Target accrual: 300 patients

Subject population (children, adults, groups): Adult males and females

Inclusion Criteria:

1. Unilateral primary TKA or THA
2. 18+ years of age
3. Able to provide informed consent

Exclusion Criteria:

1. Body mass index (BMI) > 45 kg/m^2
2. Severe drug allergy\* to medications used in this study, including non-steroidal anti-inflammatory drugs (i.e. celecoxib and ketorolac), and local anesthetics.
  - *\*defined as an immune reaction resulting in shortness of breath, hives, anaphylaxis, wheezing, and fever*
  -
3. Contraindication to spinal anesthesia technique (e.g., known spinal stenosis, coagulopathy, sepsis, infection at site of injection, uncooperative, refusal, anticoagulation medications not held within appropriate time frame\*).
  - *\*Per ASRA guidelines, Clopidogrel (Plavix) held for at least 7 days, Dabigatran (Pradexa) held for at least 5 days, Rivaroxaban (Xarelto) held for at least 3 days, Warfarin (Coumadin) held for at least 5 days or recent INR of less than 1.4, Enoxaparin (Lovenox) with doses > 1 mg/kg held for close to 24 hours.*
4. Known to be currently pregnant or actively breastfeeding++
  - *++ Patients that have a previous history of menopause, hysterectomy, or tubal ligation will not be required to perform a pregnancy test. Female patients that do not meet this criterion will be asked to submit a urine sample, and will require a negative urine sample in order to proceed with study protocol. Urine sample be collected pre-procedurally.*
5. Impaired cognition
6. Lower extremity motor deficit

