### Statistical Considerations

#### Randomization

Subjects will be randomized into one of two study groups: mepivacaine or low-dose bupivacaine. In order to ensure balance on the subject demographics between the two study groups, the subjects will be stratified on procedure (TKA vs THA), gender, age group ( $\geq 70$  vs.  $< 70$ ) and BMI ( $\geq 32$  vs.  $< 32$ ). Within each stratum, subjects will be assigned to either of the two study groups using a computerized dynamic allocation program housed in an online application developed by personnel in the Division of Biomedical Statistics and Informatics. Using dynamic allocation will ensure that the subject allocation will remain balanced on the stratification factors and the study group assignment throughout the entire subject accrual phase.

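### Pain and 24-hour opioid use are compared without regard to preoperative opioid use; stratifying by it would be a cheap precision gain for two secondary outcomes

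*Combined protocol and SAP*

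**What the plan says.** Pain and opioid use are secondary outcomes: "Secondly, we will assess a variety of both continuous and categorical outcomes between groups including pain scores, opioid consumption". Study Design and Methods, under In Hospital Evaluation, defines the opioid outcome and leaves its recording to nurses: "Additional data points to be recorded by nursing staff will be total opioid consumption in the first 24 hours after surgery, pain scores".

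The Analysis section compares continuous outcomes by t-test, or by rank-sum test if they are not close enough to normal. Pain scores, as ordinal data, get a rank-sum test. No covariate or stratum enters any comparison.

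Under Subject Information, the three inclusion criteria begin with "Unilateral primary TKA or THA" and the six exclusions end with "Lower extremity motor deficit". None of the nine concerns opioid use before surgery, opioid tolerance or chronic pain.

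Under Randomization, "the subjects will be stratified on procedure (TKA vs THA), gender, age group" and BMI. The assurance given there reaches only those factors: "subject allocation will remain balanced on the stratification factors and the study group assignment throughout the entire subject accrual phase".

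**The concern.** A patient who takes opioids before surgery may well use more of them afterwards, whichever spinal drug is given. If so, user status is a baseline predictor of the 24-hour total, and perhaps of pain, that can be known before randomization. When it is left out of the comparison, the spread between users and non-users stays in the error term. When it is also left out of the allocation, the share of users can differ between arms by chance.

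What is at stake is the width of the confidence intervals for two secondary outcomes. With no such item specified, a reader of the results might also be unable to see how users were distributed between the arms.

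**Working it through.** **The plan's own figures.** The plan states no power or precision for opioid use or pain, so there is nothing to reproduce for them. The 150 per group under Sample Size is set for motor recovery and is used here only as the planned group size. The variance shares and the percentage cuts in standard error below do not depend on it.

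**Assumed inputs (none is in the documents).** Share of users p: 10% to 30%. Ratio of users' to non-users' 24-hour total: 1.5 to 2.5. Within-group coefficient of variation: 0.75.

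**Formulas, on the log scale.**
- d = ln(ratio)
- s² = ln(1 + 0.75²) = ln(1.5625) = 0.446
- R² = p(1−p)d² / (p(1−p)d² + s²)
- Cut in standard error = 1 − √(1−R²)
- Equivalent extra patients = 1/(1−R²) − 1

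| p | Ratio | d² | p(1−p)d² | R² | Cut in SE | Equivalent extra patients |
|---|---|---|---|---|---|---|
| 10% | 1.5 | 0.164 | 0.015 | 0.03 | 1.6% | 3% |
| 20% | 2 | 0.480 | 0.077 | 0.15 | 7.6% | 17% |
| 30% | 2.5 | 0.840 | 0.176 | 0.28 | 15.3% | 40% |

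**Second parameterization.** Let users differ from non-users by k = 0.5 to 1.5 within-group standard deviations, with the same p. Then R² = p(1−p)k² / (1 + p(1−p)k²), which runs from 0.02 to 0.32. The standard error falls by 1% to 18%. Where the adjusted analysis has 80% power, the unadjusted one has between 79% and 64%. In the middle case (p = 20%, k = 1) it has 74%. The two sets of assumptions give similar answers.

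**Chance imbalance at 150 per arm and 20% users.** Under simple 1:1 randomization, the standard deviation of the arm difference in user share is √(2 × 0.2 × 0.8 / 150) = 0.046. The 95% range is therefore ±1.96 × 0.046 = ±9 percentage points. With a doubling:
- Shift in the log-scale arm difference at that limit: 0.0905 × 0.693 = 0.063.
- Unadjusted standard error: √(2 × (0.077 + 0.446) / 150) = 0.084.
- Shift in standard errors: 0.063 / 0.084 = about 0.75.

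**Validity.** In 20,000 simulated trials with 20% users, a one-SD user effect and no drug effect, the unadjusted t-test rejected in 5.07%. The nominal level is 5%.

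**Limits of these figures.** They describe a log-scale comparison. A stratified rank test should gain by a similar order, but not by exactly these amounts. For pain, the documents offer no basis for even an assumed ratio.

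**The case against.** The strongest reply is that nothing here is an error. Unadjusted t and rank-sum tests are legitimate in a randomized trial, these are two of eight secondary outcomes, and the plan sets no precision target for them that is missed. The size rests wholly on assumed values, and the low end of the range is trivial. All of this stands, and it makes the point an optional improvement. It does not remove the case for the change, because the gain costs almost nothing.

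A reader might infer more in four ways. The documents do not support any of them.

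- **That imbalance in users biases the result or passes for a drug effect.** Randomization keeps the type I error at 5%. A 1-in-20 imbalance moves the result by about 0.75 standard errors in the middle case, and the unadjusted interval already allows for that variation.
- **That preoperative opioid use will not be collected.** The list under In Hospital Evaluation covers what staff record during the stay. The Analysis section refers to preoperative data and baseline covariates without listing any. The supportable statement is that the item is not specified.
- **That the operating surgeon should be handled in the same way, as a fifth allocation factor.** The Resources text says only that "The Co-Principal Investigator orthopedic surgeons maintain high volume practices specializing in TKA and THA". It gives neither the number of surgeons nor any variation between them. Four binary factors already make 2⁴ = 16 strata, and adding a fifth is a debatable trade-off.
- **That a linear model on the log total is the natural remedy.** It is undefined for any patient with a zero 24-hour total.

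**Conclusion.** The point holds as a low-cost improvement to two secondary comparisons. Eligibility of preoperative users follows from the absence of any criterion against them. Their status is not balanced by the allocation, is not specified for collection, and is not used in the analysis. The consequence is lost precision only, and only if users do need more opioid than non-users.

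Under the main set of assumptions, the standard error for the 24-hour total would fall by about 2% to 15%, and by about 8% at 20% users and a doubling. If users are few or differ little from non-users, the gain is negligible. For pain the direction is plausible but the size is unknown. Neither the primary endpoint nor the validity of the planned tests is in question.

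**What to change.** Make two additions.

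1. In Study Design and Methods, specify preoperative opioid use (yes/no), taken from the medical record before surgery so that treatment cannot influence it.
2. In Analysis, state that the 24-hour opioid total and pain scores will be compared by a rank-sum test stratified by that variable (van Elteren). This handles zero totals as ties and needs no normality check. At 150 per arm, 10% users would still leave about 15 users in each arm (0.10 × 150), and 20% about 30.

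The allocation program, eligibility and primary analysis stay as they are. The cost is one chart item per patient and a slightly more complex secondary analysis, with no extra patients or visits. The plan already has a study coordinator and medical-record review in place.

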Total knee arthroplasty (TKA) and total hip arthroplasty (THA) are two of the most common orthopedic procedures performed in the United States, with significant growth in procedure volume expected over the coming decades. Coupled with the growing number of surgeries, is a growing cost to perform these procedures. In order to accommodate the increased demand for total joint arthroplasty (TJA) while also reducing complications and costs, optimized recovery pathways are needed to enhance resource utilization. One way to significantly impact recovery and length of stay is for patients to participate in physical therapy earlier in their episode of care. In addition to facilitating patient readiness for discharge from the hospital, early physical therapy and ambulation reduces post-operative complications such as venous thromboembolism and pneumonia. Multiple factors related to anesthesia can affect a patient's ability to participate in physical therapy on the day of surgery; these include post-operative nausea and vomiting, orthostatic hypotension and residual muscle weakness. The use of spinal anesthesia for TJA has been shown to reduce the risk of these complications. Shortening the duration of motor blockade in spinal anesthesia can reduce the time to patient physical therapy readiness, facilitating early ambulation and discharge to home.

Historically, short to intermediate duration local anesthetics such as lidocaine have been used for spinal anesthetics in short duration knee procedures such as knee arthroscopy. However, the use of lidocaine in spinal anesthesia has been dramatically reduced due to a high incidence of transient neurologic symptoms (TNS). TNS was first defined in 1993, and is defined as a painful condition of the buttocks and thighs with possible radiation to the lower extremities, beginning as soon as a few hours after spinal anesthesia and lasting as long as ten days. All local anesthetics can cause TNS but it is most commonly associated with lidocaine and reported to occur in 4% to 40% of patients undergoing spinal anesthesia with lidocaine.

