## Study Design and Methods

**Methods:** *Describe, in detail, the research activities that will be conducted under this protocol:*

**Preoperative Visit and Anesthesiologist Assessment:** Patients meeting eligibility criteria will be approached during their surgical preoperative visit by the study coordinator in the clinic of the orthopedic Co-Principal Investigators. Those choosing to participate will be screened for inclusion and exclusion criteria. Patients will be assessed for ability to undergo a spinal anesthetic, but will be counseled that the decision between a spinal and general anesthetic will ultimately be determined by the anesthesiologist on the day of surgery. Thus, patients may be withdrawn on the day of surgery if the staff anesthesiologist does not agree with their candidacy to undergo a spinal anesthetic. Furthermore, patients will be counseled they may be withdrawn from the study if placement of a spinal anesthetic in the operating room proves unsuccessful and a general anesthetic is required.

**Randomization and Blinding:** Patients will be randomized in a 1:1 fashion. The first arm will be the "Mepivacaine" (70 mg) group and the second arm will be the "Low-Dose Bupivacaine" (10 mg) group. This trial will be conducted in a double-blinded manner. The patient and the postoperative outcomes assessors (PACU and Orthopedic Inpatient Nurses and Physical Therapists) will be the blinded parties. The anesthesia and surgical teams will not be blinded given they won't be responsible for any assessments. After a patient has been consented and enrolled, the study coordinator will randomize the patient to either Mepivacaine or Low-Dose Bupivacaine using a custom electronic randomization system which will be maintained by the study statistician. The surgical team and anesthesia team will be notified after the assignment is complete so the surgical listing can be completed with the appropriate medication.

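### Time to first physical therapy could be compared a little more precisely by using the recorded start time in a rank-based analysis; the planned tests are valid.

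*Combined protocol and SAP*

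**What the plan says.** The Analysis section names time to first therapy among the continuous outcomes: "time to participation in physical therapy, and walking distance will be compared between the 2 study groups using two-sample t-tests" if the data are sufficiently normal; "otherwise non-parametric Wilcoxon rank sum tests will be used". Hospital stay falls under the same rule ("length of PACU stay and hospital stay, time to participation in physical therapy"). No covariate-adjusted or stratified analysis is planned for any outcome.

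The data for such an analysis are collected. Under Study Design and Methods, "The study will begin with the anesthesiologist recording the time the spinal anesthetic is administered", and the physical therapists are responsible for "recording the time of the first physical therapy session and the distance the patient ambulates during this session".

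Start time does not enter the allocation either. The Randomization section says "the subjects will be stratified on procedure (TKA vs THA), gender, age group" and BMI. The surgical and anesthesia teams, who are not blinded, learn the assignment "so the surgical listing can be completed with the appropriate medication".

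The background text under Research Question and Aims discusses the patient's "ability to participate in physical therapy on the day of surgery". The endpoint list contains time to therapy but not same-day therapy as such. The documents give no therapy hours, no spread of case start times, no rule for when therapy moves to the next day, and no standard deviation for time to therapy or length of stay.

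**The concern.** The practical argument for the shorter-acting drug is earlier therapy and discharge. If therapists work limited hours, time from spinal to first session falls into two clusters, same day and next morning, and the hour of surgery largely decides which one a patient joins. That variation has nothing to do with the drug. An analysis that ignores start time leaves it in the error term, so a real effect on time to therapy is harder to see. The variable that would remove part of this noise is already on the study card.

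**Working it through.** **No plan figure to reproduce.** The only design calculation is for the primary endpoint. From its inputs, n per group = 2 × (1.96 + 0.8416)² × 65.6² / 30² = 75.06, so 76, where the plan states 150. That mismatch is a separate matter and has no bearing here. I borrow three numbers from the Sample Size section: 150 per arm, a 30-minute effect and an SD of 65.6 minutes. Everything about scheduling below is assumed.

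**General result for means.** If start time explains a share R² of the outcome variance, adjustment multiplies the confidence interval width by √(1 − R²) and is worth 300/(1 − R²) patients.
- R² = 0: factor 1.000, 300 patients (no gain)
- R² = 0.10: factor √0.90 = 0.949, 333 patients
- R² = 0.30: factor √0.70 = 0.837, 429 patients

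The documents give no R² for either outcome.

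**Simulation A.** 2,000 trials per row. Assumptions: spinals spread evenly from 07:30; mean motor recovery 220 minutes (SD 65.6), 30 minutes shorter in one arm; about 60 minutes' lag to therapy; next-day sessions between 08:00 and 10:00. The latest start and the therapy closing hour were varied to change the next-day share. Time was counted from the spinal, because the plan does not define the origin. The stratified test is van Elteren's, by quartile of start time. Entries are power at two-sided 5%.

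| Next-day share | t-test | Linear model + start time | Wilcoxon (plan's fallback) | Wilcoxon stratified by start time | Rank gain |
|---|---|---|---|---|---|
| 0% | 93% | 93% | 94% | 93% | none |
| 8% | 55% | 61% | 93% | 93% | none |
| 20% | 44% | 64% | 88% | 90% | 2 points |
| 32% | 37% | 64% | 76% | 83% | 7 points |
| 40% | 30% | 56% | 62% | 73% | 11 points |

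**Simulation B.** Different assumptions: spinals 07:30 to 14:30, mean readiness 4.5 h plus an exponential wait with mean 45 minutes, next-day sessions from 08:00.

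| Therapy ends | Next-day share | Wilcoxon | Rank-based with start time | Rank gain |
|---|---|---|---|---|
| 16:00 | 50% | 57% | 65 to 68% | 8 to 11 points |
| 17:00 | 36% | 71% | 78% | 7 points |
| 19:00 | 11% | 89% | 90% | 1 point |

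In these three cases the raw-scale linear model with start time reached only 54 to 57%.

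**Which comparison matters.** With a next-day cluster the data are far from normal. In a re-run of the simulation B scenarios, a Shapiro test rejected normality in every trial. The plan's own rule then selects Wilcoxon, so the relevant comparison is Wilcoxon against Wilcoxon with start time. The t-test column describes a test the plan would not use. In every scenario with next-day cases, the adjusted linear model on raw times does no better than the unadjusted Wilcoxon, and usually much worse.

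**Validity.** With no drug effect and 36% next-day cases, rejection rates in simulation A were 4.8% to 5.3% for all methods, adjusted or not.

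**The case against.** The strongest objection is that the mechanism is not in the documents. Nothing says that late cases wait until the next day, and if nearly all patients have therapy on the day of surgery the gain is nil. The larger gains need a third to a half of patients to miss same-day therapy, and the background presents therapy that day as the goal. This stands, and it is why the gain can only be given as a range.

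Second, the Wilcoxon fallback already handles most of the problem. This also stands. A reader who stops at the t-test might infer a large loss, such as 37% power against 64%. The plan's normality rule does not support that reading.

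Third, the spinal time precedes any drug effect but follows assignment, and unblinded teams complete the listing. If the assignment influenced case order, the spinal time would not be a clean baseline covariate. This is a fair caution and shapes the fix. It does not favour the planned analysis, because a drift in case order by arm would distort the unadjusted comparison too, and nothing planned would reveal it.

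Fourth, these are secondary outcomes with no power claim, and same-day therapy appears in the background, not as an endpoint. Agreed: leaving it off the endpoint list is not an error.

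**Conclusion.** The plan collects a likely predictor of time to first therapy and does not use it. This is a missed efficiency gain of modest size on a secondary outcome, not an error. Against the test the plan would actually apply, start-time adjustment or stratification on ranks adds about 1 to 11 points of power when roughly 11% to 50% of patients have therapy the next day, and essentially nothing at 8% or fewer. These figures rest on assumed therapy hours, start times and waiting times, and on the borrowed 30-minute effect and 65.6-minute SD.

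Three stronger readings are not supported. A reader might infer that the planned tests are invalid, but their type I error stays near 5%. A reader might infer that the length-of-stay comparison loses a known amount of precision; the same variance argument applies, but no R² or SD is available and that outcome was not simulated. A reader might infer that the main result is weakened, but the primary endpoint is motor recovery and is unaffected.

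**What to change.** In the Analysis section, for time to first physical therapy:

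1. Prespecify a rank-based model with study group and start time, start time entering as a flexible term, or a Wilcoxon test stratified by start-time band (van Elteren). Do not substitute a linear model on raw times.
2. Use the scheduled start or case order if it is fixed before assignment. Otherwise use the recorded spinal time and report its distribution by arm.
3. State the time origin of the outcome.
4. Optionally apply the same adjustment to length of stay, noting that the gain is unknown.
5. Report descriptively, by arm, the share of patients with therapy on the day of surgery. It can be derived from times already recorded and adds no formal test.

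The sponsor knows its own therapy hours and case schedule, and so can judge where in the range the gain would fall. The cost is SAP wording, one or a few degrees of freedom and a little more analysis work. If the spinal time is used, no new data are needed.

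### Eight secondary outcomes are each tested at two-sided 0.05 with no hierarchy, correction or exploratory label, so the chance of at least one false significant result among them is well above 5% if all eight nulls hold

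*Combined protocol and SAP*

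**What the plan says.** The Endpoints section names one primary outcome, the time from spinal administration to Bromage 0 in the non-operative leg. Its secondary list reads "pain scores, opioid consumption, urinary retention, transient neurologic symptoms, length of PACU stay, length of hospital stay, time to participation in physical therapy and walking", the last item being how far the patient walks in therapy. This makes eight outcomes.

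The Analysis section plans formal comparisons for these: "Secondly, we will assess a variety of both continuous and categorical outcomes between groups including pain scores, opioid consumption, urinary retention, transient neurologic symptoms" and the rest of the same list. Tests are assigned by type of variable. Continuous outcomes "will be compared between the 2 study groups using two-sample t-tests if the data are sufficiently normally distributed", with the Wilcoxon rank sum test otherwise. Ordinal outcomes such as pain scores get the Wilcoxon test. For the remainder, "Binary and nominal categorical outcomes will be compared between the study groups using chi-square tests or Fisher's exact tests".

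One sentence then sets the decision rule for everything: "All statistical tests will be two-sided and the threshold of statistical significance will be set at" 0.05.

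The next paragraph adds one interim analysis, with a Lan-DeMets spending function and O'Brien-Fleming type boundaries "to maintain the overall type 1 error rate at" 0.05. The same section also promises descriptive reporting of all outcomes, with 95% confidence intervals where appropriate.

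**The concern.** The threshold sentence is a rule, not an omission. As written, it allows any one of eight secondary differences to be called statistically significant at p < 0.05. It does so whatever the other seven show and whether or not the primary comparison succeeds. Nothing in the plan says how such a finding should be read.

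Alpha spending does not fill this gap, because it deals with repeated looks at the data. Even if it is meant to cover the secondaries as well, it would hold each one at 0.05 across the two looks. It would not hold the set of eight at 0.05.

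What is at stake is the reading of the second aim in Research Question and Aims, which consists of these outcomes. A chance difference in, say, opioid use or walking distance could be reported as an established effect of the drug.

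**Working it through.** **Plan's own figure.** None exists to reproduce. The documents state no error rate for the secondary outcomes as a set.

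**Inputs from the documents**
- Per-test threshold: 0.05, two-sided, for all tests (Analysis).
- Number of named secondary outcomes: 8 (Endpoints; repeated in Analysis).

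**Inputs assumed**
- All eight null hypotheses are true, and each test has its full 5% size.
- Correlation among the test statistics: not given, so varied from 0 to 0.9.

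**Step 1. Independent tests.** The chance of at least one false significant result is 1 − (1 − 0.05)^8 = 1 − 0.6634 = 0.337, about 34%. The expected number of false significant results is 8 × 0.05 = 0.4, whatever the correlation.

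**Step 2. Common correlation ρ.** For eight standard normal statistics with the same pairwise correlation, the chance is

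1 − ∫ φ(x) · [Φ((1.96 − √ρ·x)/√(1−ρ)) − Φ((−1.96 − √ρ·x)/√(1−ρ))]^8 dx.

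Numerical integration gives:

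| Assumed ρ | At least one false significant result |
|---|---|
| 0 | 34% |
| 0.3 | 30% |
| 0.5 | 25% |
| 0.7 | 19% |
| 0.8 | 16% |
| 0.9 | 12% |

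**Step 3. Correlation in blocks.** One alternative is to let pain and opioid use correlate with each other, and the two stays, time to therapy and walking distance correlate among themselves. With 0.3 to 0.7 within blocks and 0 to 0.2 elsewhere, simulation (1,000,000 draws) gives 27% to 33%.

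**Step 4. A rare binary outcome.** A chi-square or Fisher test of a rare event falls short of its nominal size. With 150 per group and an assumed true rate of 1% for transient neurologic symptoms, the exact size is about 0.2%. Seven tests at 5% and one at 0.2% give 1 − 0.95^7 × 0.998 = 1 − 0.6983 × 0.998 = 0.303, about 30% under independence.

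**Step 5. Fewer true nulls.** If the four recovery outcomes (PACU stay, hospital stay, time to therapy, walking distance) truly differ, four nulls remain. The chance is then 1 − 0.95^4 = 1 − 0.8145 = 0.185, about 18.5% under independence.

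**Step 6. More than eight tests.** The list is introduced as a set of examples, pain has no stated time point, and In Hospital Evaluation also records nausea or vomiting and orthostatic hypotension. If ten tests were run (an assumption), independence gives 1 − 0.95^10 = 0.401, about 40%, and a common correlation of 0.5 gives about 29%.

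Every scenario computed here lies well above 5%. The exact value depends on assumptions that the documents cannot settle.

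**The case against.** The strongest reply is that the plan has a clear primary outcome. The only stated hypothesis concerns motor recovery, the sample size rests on that outcome alone, and the secondaries are consistently named as such. The error rate of the primary is untouched. Testing secondaries without correction is common when they are read as supportive, and the plan already promises confidence intervals. All of this stands, and it limits the severity. It does not close the gap, because the plan never says that the secondaries are supportive. Descriptive reporting is promised for all outcomes, the primary included, and formal tests with a significance threshold are then added on top.

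A second reply is that the size of the inflation is uncertain. That also stands. It assumes that all eight nulls hold, while the plan's own background expects shorter motor block to speed therapy and discharge. A reader might take about 25% as the figure, but it needs a common correlation of 0.5, which the documents do not give.

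Other stronger readings also go too far:
- A reader might infer that the plan puts secondaries on the same footing as the primary. They share a threshold, but the plan keeps the two roles apart throughout.
- A reader might infer that hospitals would choose between the drugs on these outcomes. The documents tie no decision to them.
- A reader might infer that the promise of an overall rate of 0.05 is false. That sentence concerns the timing of the interim look and makes no claim about the number of outcomes.

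**Conclusion.** The concern holds as a modest flaw in the decision rule. Under the written threshold, and if all eight secondary nulls are true, the chance of at least one false significant secondary result is about 34% for independent tests. It falls with correlation, to about 25% at an assumed 0.5 and about 12% at an assumed 0.9. It is also lower if some secondaries truly differ or if a rare outcome is tested below its nominal size. That the rate exceeds 5% does not hinge on any one of the correlations examined; its exact value does. The validity of the primary comparison is not in question.

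**What to change.** In the Analysis section, replace the threshold sentence with:

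> The two-sided 0.05 significance threshold, with the interim spending function, applies to the primary outcome only. All secondary outcomes are exploratory: between-group differences are reported with 95% confidence intervals and unadjusted two-sided p-values, and none will be declared statistically significant.

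This takes two sentences and no new data, patients or analyses. Every estimate, interval and p-value is still reported, so a possible harm signal, such as transient neurologic symptoms or urinary retention, remains as visible as before. The downside is that a lone secondary p-value below 0.05 can no longer be claimed as a significant finding.

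A formal correction is not proposed. At 0.05/8 = 0.00625 per test the rate under independence would fall to 1 − 0.99375^8 = 4.9%. However, with 150 per group and an assumed effect of 0.4 SD, the power of a single secondary test would fall from 93% to 77%. The plan would also need a rule for secondary testing at the interim look.
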